9.6.2 Statistical Methods for Safety Analyses

Safety and tolerability will be assessed by clinical review of all relevant parameters, including AEs and postvaccination temperature measurements.

Consistency of the safety profile across lots will be assessed via point estimates and 95% CIs (for select safety endpoints) within each of the V114 vaccination groups (Lot 1, Lot 2, Lot 3). Details will be provided in the sSAP. The analysis of safety will then be performed for V114 overall (combining the Lot 1, Lot 2, and Lot 3 vaccination groups) versus the Prevnar 13™ vaccination group following a tiered approach as detailed below (Table 5).

The tiers differ with respect to the analyses that will be performed. AEs (specific terms as well as system organ class [SOC] terms) are either pre-specified as “Tier 1” endpoints or will be classified as belonging to "Tier 2" or "Tier 3" based on the number of events observed.

Tier 1 Events

Safety parameters or AEs of special interest that are identified a priori constitute “Tier 1” safety endpoints that will be subject to inferential testing for statistical significance with p-values and 95% CIs to be provided for between-treatment differences in the proportion of participants with events; these analyses will be performed using the Miettinen and Nurminen (M&N) method [Miettinen, O. and Nurminen, M. 1985], an unconditional, asymptotic method. For this protocol, solicited injection-site AEs (redness/erythema, swelling, and tenderness/pain) from Day 1 through Day 5 postvaccination and solicited systemic AEs (muscle pain/myalgia, joint pain/arthralgia, headache, and tiredness/fatigue) from Day 1 through Day 14 postvaccination are considered Tier 1 events.

Tier 2 Events

Tier 2 parameters will be assessed via point estimates with 95% CIs provided for differences in the proportion of participants with events (also via the M&N method) [Miettinen, O. and Nurminen, M. 1985].

Membership in Tier 2 requires that at least 36 participants in the V114 combined group (combining Lot 1, Lot 2, and Lot 3 vaccination groups) or 4 participants in the Prevnar 13™ group exhibit the event. Because many 95% CIs for Tier 2 events may be provided without adjustment for multiplicity, the CIs should be regarded as a helpful descriptive measure to be used in review, not a formal method for assessing the statistical significance of the between-group differences in AEs.

In addition, the broad AE categories consisting of the proportion of participants with any AE, a vaccine-related AE, an SAE, a vaccine-related SAE, and death will be considered Tier 2 endpoints. Nonserious adverse events (NSAEs) will be followed for 14 days postvaccination and SAEs will be followed for 6 months postvaccination. The proportion of participants with maximum temperature measurements meeting the Brighton Collaboration cut points will also be considered Tier 2 endpoints.

Tier 3 Events

Safety endpoints that are not Tier 1 or 2 events are considered Tier 3 events. Only point estimates by treatment group are provided for Tier 3 safety parameters.

Table 5 Analysis Strategy for Safety Parameters

Safety Tier	Safety Endpoint [†]	p-Value [‡]	95% CI for Between-Group Comparison [‡]	Descriptive Statistics
Tier 1	Injection-site redness/erythema (Days 1 to 5)	X	X	X
	Injection-site swelling (Days 1 to 5)	X	X	X
	Injection-site tenderness/pain (Days 1 to 5)	X	X	X
	Muscle pain/myalgia (Days 1 to 14)	X	X	X
	Joint pain/arthritis (Days 1 to 14)	X	X	X
	Headache (Days 1 to 14)	X	X	X
	Tiredness/fatigue (Days 1 to 14)	X	X	X
Tier 2	Any AE [†]		X	X
	Any Vaccine-Related AE [†]		X	X
	Any SAE [†]		X	X
	Any Vaccine-Related SAE [†]		X	X
	Death [†]		X	X
	Maximum temperature measurements meeting the Brighton Collaboration cut points (Days 1 to 5)		X	X
	Specific AEs by SOC and PT [§] (incidence ≥36 participants in the combined V114 group or ≥4 participants in the Prevnar 13 TM group)		X	X
Tier 3	Specific AEs by SOC and PT [§] (incidence <36 participants in the combined V114 group and <4 participants in the Prevnar 13 TM group)			X
[†] These endpoints are broad AE categories. For example, descriptive statistics for the safety endpoint of “Any AE” will provide the number and percentage of participants with at least 1 AE. [‡] These analyses will be performed using the M&N method [Miettinen, O. and Nurminen, M. 1985]. [§] Includes only those endpoints not prespecified as Tier 1 or not already prespecified as Tier 2 endpoints. AE = adverse event; CI = confidence interval; M&N = Miettinen and Nurminen; PT = preferred term; SAE = serious adverse event; SOC = system organ class; X = results will be provided.				

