4.2 Scientific Rationale for Study Design

This study will serve as a lot-to-lot consistency study for licensure of V114. This study is conducted to demonstrate the consistency of the antibody response to 3 different

manufactured lots of V114 in a population (ie, healthy adults ≥ 50 years of age) at elevated risk for pneumococcal disease and its associated morbidity and mortality. Prevnar 13™ was included as the active comparator in this study to better characterize the safety profile of V114.

The incidence of IPD is directly related to age, with over half of all cases occurring in adults 50 years of age or older [Drijkoningen, J. J 2014]. The population of subjects included in this study (healthy adults ≥ 50 years of age) is consistent with the indication of pneumococcal vaccines, including Prevnar 13™, in healthy adults.

Demonstration of lot-to-lot consistency is often required by some national regulatory agencies prior to licensure of investigational vaccines. The objective of a clinical lot-to-lot consistency study is to show consistency of manufacturing and clinical performance of the final product by demonstrating that 3 consecutively manufactured final formulated clinical lots of the vaccine display comparable safety profiles and elicit equivalent immune responses. The sample size of this study will allow for a high statistical probability to demonstrate consistency of the immune response across 3 lots of V114, while also bolstering the size of the overall safety database of the clinical development program.

Participants will be stratified by age group based on observations from previous V114 adult studies, where individuals ≥ 75 years of age showed lower post-vaccination immunogenicity responses (based on OPA response) for several serotypes compared with individuals 50 to 64 and 65 to 74 years of age.

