6.3.2 Stratification

Intervention allocation/randomization will be stratified according to the following factors:

- Age at time of randomization:
 - Participants 50 to 64 years of age
 - Participants 65 to 74 years of age
 - Participants ≥ 75 years of age.

Approximately 50% of the participants will be ≥ 65 years of age.

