9 STATISTICAL ANALYSIS PLAN

This section outlines the statistical analysis strategy and procedures for the study. If, after the study has begun, but prior to any unblinding/final database lock, changes are made to hypotheses, or the statistical methods related to those hypotheses, then the protocol will be amended (consistent with International Council for Harmonisation [ICH] Guideline E-9). Changes to other non-confirmatory analyses made after the protocol has been finalized, but prior to unblinding/final database lock, will be documented in a supplemental Statistical Analysis Plan (sSAP) and referenced in the Clinical Study Report for the study. Post hoc exploratory analyses will be clearly identified in the Clinical Study Report.

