9.10 Subgroup Analyses

To determine whether the intervention effect is consistent across various subgroups, the estimate of the between-group treatment effect (with a nominal 95% CI for each V114 vaccination group) will be summarized for the primary immunogenicity endpoint. The 95% CI will only be calculated if there are more than 10 participants in each vaccination group for each subgroup. In addition, a summary of AEs and a summary of solicited AEs will be provided for each subgroup (point estimates only) for V114 overall (combining the Lot 1, Lot 2, and Lot 3 vaccination groups) and the Prevnar 13™ vaccination groups. The following are examples of classification variables:

- Age category (50 to 64 years, 65 to 74 years, and ≥75 years)
- Race (eg, White, Black, Asian, and Other)
- Sex (female, male)

Further details of subgroup analyses will be documented in the sSAP.

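### The Tier 1 solicited-AE comparisons do not use the age strata of the randomisation: a valid analysis that leaves a small gain in precision unused

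*Combined protocol and SAP*

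**What the plan says.** Section 6.3.2: "Intervention allocation/randomization will be stratified according to the following factors", followed by age at randomisation in three groups, 50–64, 65–74 and 75 or over. About half of participants are to be 65 or older. Section 4.2 gives the reason: in earlier V114 adult studies the oldest group "showed lower post-vaccination immunogenicity responses (based on OPA response) for several serotypes". It says nothing about AE rates by age.

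Section 9.6.2: "The analysis of safety will then be performed for V114 overall (combining the Lot 1, Lot 2, and Lot 3 vaccination groups) versus the" Prevnar 13 group. For Tier 1 events (three injection-site and four systemic solicited AEs), which receive p-values and 95% CIs, "these analyses will be performed using the Miettinen and Nurminen (M&N) method". No strata or stratum weights are named there, in the section 9.1 summary or in Table 5. Section 9.6.2 refers to the sSAP only for consistency of safety across lots.

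Age is used elsewhere. The cLDA model in section 9.6.1 has terms for age stratum and age stratum by time, and a similar model serves the IgG comparison of combined V114 with Prevnar 13. For solicited AEs, age appears only in the section 9.10 subgroup summaries, as point estimates.

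**The concern.** When randomisation is stratified by a factor that predicts the outcome, the chance imbalance due to that factor is largely removed by design. A crude analysis still counts the between-stratum variation in its standard error, so it overstates the uncertainty. The result is a test somewhat below its nominal level and intervals somewhat too wide.

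Solicited AEs belong to a primary objective, and the Tier 1 events are the only safety endpoints given p-values. Precision is limited by the 220 Prevnar 13 participants. In a safety comparison a conservative test offers no protection; it slightly lowers the chance of seeing a real difference. M&N can also be run with or without strata, so saying which in advance fixes a single result per endpoint.

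**Working it through.** **Inputs from the documents.** 2000 V114 and 220 Prevnar 13 participants, all evaluable for safety, 2-sided 5% level (section 9.9.2); about 50% aged 65 or over (sections 4.1 and 6.3.2).

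**Assumptions.** The share aged 75 or over is not given; I take 15%, with 10% and 25% as the range. All age-specific AE rates are assumed.

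**The plan's own figure.** Table 6 gives detectable differences at about 80% power by an unstratified two-proportion method. With the group sizes as labelled, the Farrington–Manning formula at a zero null difference gives power of 26.9% to 78.0% over the seven rows. With the two sizes interchanged it gives 79.7% to 80.9%. That is a separate matter, and nothing below depends on Table 6 being right.

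**Precision.** For stratum shares w and rates p, with pooled rate p̄ = Σwp:

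- variance ratio r = Σwp(1−p) / [p̄(1−p̄)]
- CI narrowing = 1 − √r
- crude half-width = 1.96 × √[p̄(1−p̄)(1/2000 + 1/220)]; the stratified one uses Σwp(1−p) instead

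Example, shares 50/35/15% and rates 75/55/40%: p̄ = 0.375 + 0.1925 + 0.06 = 0.6275; p̄(1−p̄) = 0.23374; Σwp(1−p) = 0.5×0.1875 + 0.35×0.2475 + 0.15×0.24 = 0.216375; r = 0.926. With 1/2000 + 1/220 = 0.0050455, the half-width goes from 6.73 to 6.48 points.

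**Power.** Under stratified randomisation the crude difference already has approximately the smaller variance; only its estimated standard error is too large. If the crude test has 80% power, the stratified test therefore has Φ[0.842 + 1.96(1/√r − 1)]. For r = 0.926 this is Φ(0.919) = 82.1%.

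| Shares (%) | Assumed rates (%) | r | CI narrower | Power gain (points) |
|---|---|---|---|---|
| 50/35/15 | 50/50/50 | 1.000 | 0% | 0 |
| 50/35/15 | 60/55/50 | 0.995 | 0.3% | 0.2 |
| 50/35/15 | 65/55/45 | 0.978 | 1.1% | 0.6 |
| 50/35/15 | 75/55/40 | 0.926 | 3.8% | 2.1 |
| 50/40/10 | 75/55/40 | 0.935 | 3.3% | 1.8 |
| 50/25/25 | 75/55/40 | 0.909 | 4.7% | 2.6 |
| 50/35/15 | 30/20/12 | 0.975 | 1.3% | 0.7 |
| 50/35/15 | 12/10/6 | 0.995 | 0.2% | 0.1 |

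**Simulation of the two tests.** 200,000 replicates, strata 1000/700/300 versus 110/77/33, crude against CMH-weighted stratified M&N score test:

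| Rates (%) | Type I error, crude / stratified | Power, crude / stratified (common risk difference) |
|---|---|---|
| 50/50/50 | 0.0504 / 0.0503 | 80.9% / 80.9% (9.9 points) |
| 65/55/45 | 0.0473 / 0.0499 | 83.0% / 83.5% (9.8 points) |
| 75/55/40 | 0.0414 / 0.0496 | 84.6% / 86.5% (9.6 points) |

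A second set of simulations took overall rates from Table 6 and several age gradients. Type I error was 0.037 to 0.050 for the crude test and 0.045 to 0.051 for the stratified one. At 28.3% versus 20%, with Prevnar 13 rates of about 24/18/10% by age and a 50/35/15 split, power was 77.0% crude and 77.8% stratified.

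**The case against.** The strongest reply is that there is no defect. The crude analysis is valid, the safety objective has no hypothesis or margin, safety is judged by clinical review, and no success criterion depends on these p-values. The gain requires AE rates to vary with age, which the documents do not show, and every non-zero figure rests on an assumed gradient. At rates within the range of Table 6 the effect is smaller still: half-widths go from 5.93 to 5.85 points (30/20/12%) or 4.25 to 4.24 (12/10/6%). In simulation at these rates, crude and stratified tests reached different decisions in only 0.6% and 0.15% of trials. Stratifying Tier 1 alone also puts two estimators in Table 5, and a CMH-weighted difference need not equal the difference of the two percentages shown beside it. Finally, the sSAP is not available and might name strata.

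Most of this stands, and it is why the point is minor and framed as an improvement. It does not remove the point. The smaller effects lie within the 0% to 3.8% range above, the mixed estimators need only a footnote, and the plan does not refer this choice to the sSAP. A sponsor who prefers the simple difference could instead state that Tier 1 M&N is deliberately unstratified.

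**Conclusion.** The point holds as a minor efficiency improvement. The Tier 1 comparisons name no strata although the randomisation has them, and no planned safety inference uses age. The crude analysis is unbiased and keeps its type I error at or below about 5%. What is forgone is 0% to 3.8% of CI width and 0 to 2.1 points of power with 15% aged 75 or over, rising to 4.7% and 2.6 points with 25% in that group and the steepest gradient in the first table. If solicited AE rates do not depend on age, the gain is zero. These sizes rest on assumed age-specific rates and an assumed share aged 75 or over.

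**What to change.** Add to section 9.6.2 (Tier 1 Events), with matching words in section 9.1 and a footnote to the Tier 1 rows of Table 5:

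> Tier 1 p-values and 95% CIs for V114 combined minus Prevnar 13 use the M&N method stratified by the three randomisation age groups, with Cochran-Mantel-Haenszel weights. If either group has 10 or fewer participants in a stratum, that stratum is pooled with the adjacent one (75 and over with 65–74).

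The threshold reuses the headcount rule of section 9.10: "The 95% CI will only be calculated if there are more than 10 participants in each vaccination group for each subgroup". It depends on headcount and not on events, and is fixed before unblinding. It is not expected to apply: at a share of 10% to 25% aged 75 or over, Prevnar 13 would have about 22 to 55 such participants (220 × 0.10 and 220 × 0.25). The footnote should say that the weighted difference may differ slightly from the difference of the displayed percentages. Leave the descriptive Tier 2 intervals unstratified.

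The cost is a short insertion, a footnote and a programming option, with no new participants or data. Because the safety objective carries no hypothesis, section 9 allows the change before unblinding without a protocol amendment; such changes "will be documented in a supplemental Statistical Analysis Plan (sSAP) and referenced in the Clinical Study Report".

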9.1 Statistical Analysis Plan Summary

Key elements of the statistical analysis plan are summarized below; the comprehensive plan is provided in Section 9.2 to Section 9.12.

Study Design Overview	A Phase 3, Multicenter, Randomized, Double-blind, Active Comparator-controlled, Lot-to-Lot Consistency Study to Evaluate the Safety, Tolerability, and Immunogenicity of V114 in Healthy Adults 50 Years of Age or Older (PNEU-TRUE)
Treatment Assignment	Participants will be randomly assigned in a 3:3:3:1 ratio into 1 of 4 vaccination groups: V114 Lot 1, V114 Lot 2, V114 Lot 3, or Prevnar 13™. Randomization will be stratified into 3 groups based on the participant's age (50 to 64 years of age, 65 to 74 years of age, and ≥75 years of age) at the time of randomization as described in Section 6.3.2.
Analysis Populations	Immunogenicity: Per-Protocol (PP) Safety: All Participants as Treated (APaT)
Primary Endpoint(s)	Immunogenicity: 
 Serotype-specific OPA GMTs for the 15 serotypes in V114 at 30 days postvaccination (Day 30) Safety: 
 Proportion of participants with solicited injection-site AEs (redness/erythema, swelling, and tenderness/pain) from Day 1 through Day 5 postvaccination Proportion of participants with solicited systemic AEs (muscle pain/myalgia, joint pain/arthralgia, headache, and tiredness/fatigue) from Day 1 through Day 14 postvaccination Proportion of participants with vaccine-related SAEs from Day 1 to Month 6 postvaccination
Key Secondary Endpoints	Immunogenicity: 
 Serotype-specific IgG GMCs for the 15 serotypes in V114 at 30 days postvaccination (Day 30)

Statistical Methods for Key Immunogenicity Analyses
	
Immunogenicity analyses will be conducted for each of the 15 pneumococcal serotypes in V114.
 
Each possible pairwise comparison of lots will be made (Lot 1 to Lot 2, Lot 1 to Lot 3, and Lot 2 to Lot 3). Each pairwise comparison of lots will consist of two 1-sided tests at the $\alpha=0.025$ level. Rejecting the null hypothesis of nonequivalence for any test is equivalent to requiring the bounds of the 95% CI on the pairwise lot-to-lot comparison of the V114 GMT ratios to be between 0.5 and 2.0.
 
Estimation of the serotype-specific OPA GMT ratios and 95% CIs will be conducted using the constrained longitudinal data analysis (cLDA) method [Liang, K-Y and Zeger, S. L. 2000].

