9.9.2 Sample Size and Power for Safety Analyses

The probability of observing at least 1 SAE in this study depends on the number of participants vaccinated and the underlying incidence of participants with an SAE in the study population. Calculations below assume that 100% of the randomized participants will be evaluable for safety analyses. There is an 80% chance of observing at least 1 SAE among 2000 participants in V114 group (Lot 1, Lot 2, Lot 3 combined) if the underlying incidence of an SAE is 0.08% (1 of every 1243 participants receiving the vaccine). There is a 50% chance of observing at least 1 SAE among 2000 participants in the V114 group if the underlying incidence of an SAE is 0.03% (1 of every 2885 participants receiving the vaccine). If no SAEs are observed among 2000 participants, this study will provide 97.5% confidence that the underlying percentage of participants with an SAE is <0.18% (1 in every 542 participants) in the V114 group (Lot 1, Lot 2, Lot 3 combined).

Table 6 summarizes the percentage point differences between the 2 vaccination groups that could be detected with 80% probability for a variety of hypothetical underlying incidences of an AE.

Table 6 Differences in the Incidence of Adverse Event Rates Between the 2 Vaccination Groups That Can be Detected With an Approximately 80% Probability

Incidence of Adverse Event		Risk Difference
V114 (%) N=2000	Prevnar 13™ (%) N=220	Percentage Points
1.5	0.1	1.4
5.4	2.0	3.4
9.9	5.0	4.9
16.5	10.0	6.5
22.5	15.0	7.5
28.3	20.0	8.3
39.3	30.0	9.3

The incidences presented here are hypothetical and do not represent actual adverse experiences in either group. The incidences assume a 2-sided 5% alpha level, with sample sizes of 2000 participants in the V114 group (Lot 1, Lot 2, Lot 3 combined) and 220 participants in the Prevnar 13™ group. No multiplicity adjustments were made.
 The calculations are based on an asymptotic method proposed by Farrington and Manning (1990) [Farrington, C. P. 1990].

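### The M&N 95% CIs planned for SAEs, vaccine-related SAEs, deaths and temperature cut points have tails unbalanced in V114's favour when events are few at 2000 versus 220

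*Combined protocol and SAP*

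**What the plan says.** Section 9.1 lists as a primary safety endpoint: "Proportion of participants with vaccine-related SAEs from Day 1 to Month 6 postvaccination". Section 9.6.2 compares V114 overall with Prevnar 13 in tiers. Under Tier 1 it describes the Miettinen and Nurminen (M&N) method as "an unconditional, asymptotic method"; for Tier 2 it provides "95% CIs provided for differences in the proportion of participants with events (also via the M&N method".

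A specific AE term reaches Tier 2 only with "at least 36 participants in the V114 combined group" or 4 in the Prevnar 13 group; below both it is Tier 3 and gets no interval. That filter does not apply to the broad categories: any AE, a vaccine-related AE, "an SAE, a vaccine-related SAE, and death will be considered Tier 2 endpoints". Temperature cut points are Tier 2 on the same footing. Table 5 schedules a between-group 95% CI for each and names no sparse-data alternative.

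Section 9.6.2 also says of Tier 2 that "the CIs should be regarded as a helpful descriptive measure to be used in review, not a formal method for assessing the statistical significance". Section 9.9.2 plans "with sample sizes of 2000 participants in the V114 group (Lot 1, Lot 2, Lot 3 combined) and 220 participants in the Prevnar 13™ group", and states that zero SAEs among 2000 would give "97.5% confidence that the underlying percentage of participants with an SAE is <0.18" per cent.

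**The concern.** M&N relies on the score statistic being close to normal. With a 9:1 split and very few events it is strongly skewed: one event moves the Prevnar 13 proportion by 1/220 = 0.45 points but the V114 proportion by only 1/2000 = 0.05 points. One comparator event can therefore push the whole interval below zero, while many V114 events with none on Prevnar 13 cannot push it above zero.

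These limits will be reported for a primary endpoint and for deaths. A reader who sees an interval wholly below zero will take it as fewer events on V114. Section 9.9.2 expresses rare-event safety through a one-sample bound for V114, but Table 5 schedules no interval for combined V114 alone.

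**Working it through.** **Inputs.** n1 = 2000 and n2 = 220 (Section 9.9.2 and Table 6), N = 2220, two-sided 95%, all participants evaluable (Section 9.9.2). Differences are V114 minus Prevnar 13.

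**The plan's own figures.** All three reproduce.
- 80% chance of at least one SAE: 1 - 0.20^(1/2000) = 0.0804% (plan: 0.08%, 1 in 1243).
- 50% chance: 1 - 0.50^(1/2000) = 0.0347% (plan: 0.03%, 1 in 2885).
- Zero-event bound: 1 - 0.025^(1/2000) = 0.184% (plan: 0.18%, 1 in 542). This is the Clopper-Pearson upper limit.

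**M&N interval.** It contains every d with |z(d)| < 1.96, where z(d) = (x1/n1 - x2/n2 - d) / sqrt(V), V = [p1(1-p1)/n1 + p2(1-p2)/n2] × N/(N-1), and p1, p2 are the maximum-likelihood estimates under p1 - p2 = d.

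For 0 against 1 at d = 0, p1 = p2 = 1/2220 and V = 0.00045045 × 0.99955 × 0.0050455 × 2220/2219 = 2.273 × 10^-6. The root is 0.0015076, so z = -0.0045455/0.0015076 = -3.02.

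**Skewness-corrected score interval.** Replace z by the solution z* of z = z* + g(z*² - 1), where g = m/(6V^1.5) and m = p1(1-p1)(1-2p1)/n1² - p2(1-p2)(1-2p2)/n2². For 0 against 1 at d = 0, g = -0.447 and z* = -1.88. Check: -1.88 - 0.447 × (1.88² - 1) = -3.01, which matches up to rounding.

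| V114 vs Prevnar 13 events | M&N 95% CI, points | Skewness-corrected |
|---|---|---|
| 0 vs 1 | -2.53 to -0.08 | -2.18 to +0.03 |
| 12 vs 4 | excludes zero (z = -2.03) | includes zero (z* = -1.79) |
| 2 vs 2 | -3.16 to -0.12 | still just excludes zero (z* = -2.01) |
| 26 vs 0 | includes zero (z = 1.70) | includes zero (z* = 1.94) |
| 27 vs 0 | includes zero (z = 1.73) | first to exclude zero (z* = 1.98) |
| 34 vs 0 | -0.02 to +2.37 | excludes zero |
| 35 vs 0 | first to exclude zero, +0.03 to +2.42 | excludes zero |

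**Tail errors under equal true rates.** These sum Binomial(2000, p) × Binomial(220, p) probabilities over all outcomes whose interval excludes zero. Nominal is 2.5% on each side.

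| True rate | M&N below / above zero | Corrected below / above zero |
|---|---|---|
| 0.03% | 3.6% / 0 | 0.2% / 0 |
| 0.08% | 4.3% / 0 | 1.1% / 0 |
| 0.18% | 4.2% / 0 | 2.3% / 0 |
| 0.5% | 3.9% / <0.01% | 2.2% / <0.01% |
| 1% | 3.8% / 0.02% | 2.5% / 0.8% |
| 2% | 3.4% / 1.1% | 2.5% / 2.2% |
| 5% | 3.0% / 1.7% | 2.5% / 2.4% |

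The M&N total is below 5% in every row; the largest is about 4.8%, at 5% incidence.

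**Is 35 against 0 caused by M&N?** Fisher's exact test needs 34 events against 0/220 with its two-sided p (0.043). With a one-sided level of 0.025 it needs 36 (35 gives 0.0252, 36 gives 0.0226). The threshold is essentially the same, so its main source is the 220-person comparator.

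**The case against.** The strongest reply is that little depends on these limits. Tier 2 intervals are declared descriptive, Table 5 gives no p-value for SAEs or deaths, Section 3 states no safety hypothesis, safety rests on clinical review, and an external DMC sees unblinded data. All of that stands, and it keeps this from being a failed formal test. But the plan's reason for the descriptive label is multiplicity, not inaccuracy at low counts, and the label does not correct a misplaced limit.

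Several stronger readings are tempting, and the documents do not support them.
- A reader might infer that the intervals under-cover. At zero difference they do not: total error is below 5% at every rate checked.
- A reader might take 35 against 0 as an M&N defect. Fisher's 34 to 36 shows that it is mainly the small comparator.
- Given exactly one event in the whole trial and equal risk, it falls on Prevnar 13 with probability 220/2220 = 9.9%. That is conditional: the unconditional chance of 0 against 1 peaks at about 3.7% and is 3.0% at a rate of 0.08%.
- A reader might say that Section 9.9.2 promises an analysis that Table 5 omits. Section 9.9.2 is a statement of planning precision, and Section 9.6.2 does foresee within-lot CIs for select safety endpoints, with details in the sSAP. What is not scheduled is an interval for the three lots combined.
- An exact unconditional interval looks like the natural repair. Inverting two one-sided tests over the full nuisance range gives p = 0.0405 for 0 against 1, so zero is included, but the threshold for a V114 excess moves from 35 to 80 against 0. Inverting one two-sided 5% test still excludes zero at 0 against 1, because 0.0405 < 0.05.

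**Conclusion.** The point holds as a tail imbalance. For sparse Tier 2 endpoints at 2000:220, the M&N interval lies wholly on V114's favourable side in 3.6% to 4.3% of trials with equal true rates of 0.03% to 1%, against a nominal 2.5%, and wholly on the unfavourable side in at most 0.02%. The imbalance eases to 3.4% / 1.1% at 2% and 3.0% / 1.7% at 5%. It affects a primary safety endpoint, any SAE, death, rare temperature categories and low-incidence Tier 2 terms. Specific AE terms in Tier 3 are untouched.

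This assumes the planned group sizes with everyone evaluable, and equal true risk. The documents give no expected SAE rate; 0.03%, 0.08% and 0.18% come from the illustrative calculations in Section 9.9.2, and the higher rates extend the range. The conclusion does not extend to under-coverage, nor to blaming M&N for the weak power to show a V114 excess.

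**What to change.** In Section 9.6.2, Table 5 and the Section 9.1 summary:

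(a) For all Tier 2 differences, chosen in advance and not by observed count, replace plain M&N with the skewness-corrected score interval of M&N type. It includes zero for 0 against 1 and for 12 against 4, first excludes zero at 27 against 0, and keeps each tail at about 2.5% or less. It does not cure every sparse table (2 against 2 still just excludes zero), and it cannot make up for 220 comparators. Tier 1 can stay on M&N.

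(b) For any SAE, vaccine-related SAE and death, add a Clopper-Pearson 95% CI for combined V114. This delivers the bound cited in Section 9.9.2 (0/2000 gives 0.184%) without leaning on the comparator. Section 9.6.1 already uses this method for dichotomous immunogenicity endpoints.

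The cost is wording, a less common software option for (a), and slightly less favourable upper limits for V114. No new data are needed. Safety carries no hypothesis in Section 3, so the change appears to fit the route in Section 9 for non-confirmatory analyses, provided it is documented before unblinding.
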